### **Measurements:**

The following instruments (Appendix C) will serve as outcome measures for this

## ORAL HEALTH EDUCATION SENIORS

study:

- Oral Health Related Quality of Life: The Short-Form Oral Health Impact Profile (OHIP-14; Slade, 1997) is a 14-item self-report measure that assesses individuals' perceptions of the social impact of oral conditions on their well-being. This scale evaluates the consequences of oral conditions across dimensions of functional limitation, physical pain, psychological discomfort, physical disability, psychological disability, social disability, and handicap. Items are rated on a 5-point Likert-type scale ranging from 0 (*never*) to 4 (*very often*), regarding how frequently impact has been experienced. The total score ranges from 0 to 56; higher OHIP-14 scores indicate greater impact, hence poorer oral-health-related quality of life. The OHIP-14 has been validated in two national surveys of populations in the UK and Australia (Kelly et al., 1998; Steele et al., 2004) and demonstrated good reliability, construct and discriminant validity, and internal consistency (Slade & Spencer, 1994; Slade, 1997).
- Self-efficacy will be assessed based on a modified version of an instrument developed by Finlayson and colleagues (Finlayson et al, 2007). It will be measured using a 6-item scale, asking participants to indicate how confident they feel about their ability to brush their teeth at night when they were: (1) under a lot of stress; (2) depressed; (3) anxious; (4) feeling that they were too busy; (5) tired or; (6) worried about other things in their life. The four response options range from 'very confident' to 'not at all confident'. The possible score range is 0 to 24, with high scores indicating high self-efficacy. Alpha was 0.91. Self-efficacy will be dichotomized based on a median split, with low self-efficacy pertaining to scores of 0 to 11 and high self-efficacy pertaining to scores of 12+.
- Oral Health Knowledge: A 15-item questionnaire with a three-point Likert Scale (yes, no, and don't know) will be used to assess the oral health information/knowledge of the seniors pre and post intervention. Its respective psychometric properties (validity and reliability) have already been reported (Khanagar et al, 2014).
- Demographic Factors Questionnaire will identify key demographic factors such as age, sex, race, ethnicity, education and income level of seniors.

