#### **Inclusion criteria**

##### **Patients:**

- 1) Must be 55 years old or older.
- 2) May be new, regular, emergency patients attending the TUKSoD clinic at Kleinlife or clinics at the Dental School or utilizing medical and social services at Kleinlife who have the intention to become patients of record at the dental clinic.

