**Oral Health Self Efficacy Scale**

Seniors oral health self-efficacy measure:

*Oral Health Self-efficacy (OHSE) - Scale: 4=very confident, 1=not at all confident.*

1. under a lot of stress
2. depressed
3. anxious
4. feeling like you do not have the time (too busy)
5. tired
6. worrying about other things in your life
7. bothered by your crying child
8. bothered because your child doesn't stay still when you want him or her to brush

ORAL HEALTH EDUCATION SENIORS

9. told by your child that he/she does not feel like brushing right now

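### Self-efficacy primary outcome: the Appendix C form prints nine items where the text defines six, and the stated 0–24 range should be 6–24

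*Combined protocol and SAP*

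**What the plan says.** Section 7d (Data Analysis) names the OHIP-14 and self-efficacy scores as primary outcomes and analyses both as continuous variables in repeated-measures mixed models.

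Section 7d (Measurements) introduces the instruments with a pointer to the appendix: "The following instruments (Appendix C) will serve as outcome measures for this" study. For self-efficacy it then says:

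- "Self-efficacy will be assessed based on a modified version of an instrument" from a cited earlier study, whose title in the References concerns mothers and young children's brushing.
- "It will be measured using a 6-item scale, asking participants to indicate how confident they feel about their ability to brush their teeth" at night in six listed circumstances: stress, depression, anxiety, lack of time, tiredness and other worries.
- There are four response options.
- "The possible score range is 0 to 24, with high scores indicating high self-efficacy".
- The score is dichotomised by what is called a median split, with 0–11 low and 12 or more high.

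The Appendix C form (Oral Health Self Efficacy Scale), labelled as the seniors' measure, gives the coding as "Scale: 4=very confident, 1=not at all confident" and lists nine items. Items 1–6 match the six in the text. Item 7 is "bothered by your crying child", item 8 concerns a child who will not keep still for brushing, and item 9 is "told by your child that he/she does not feel like brushing right now".

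Section 7b (Inclusion criteria) requires that a participant "Must be 55 years old or older".

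**The concern.** Two descriptions of the same primary outcome disagree, and the stated range fits neither.

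- **Item count.** The text has six items about the participant's own tooth brushing. The form has three more, all about the respondent's child, and items 8 and 9 concern the child's brushing. People aged 55 or older will often have no young child at home, so the three items probably do not apply to many of them. They look like remnants of the cited maternal instrument. Both of these statements are inferences.
- **Range.** A total of 0 cannot come from a complete form whose lowest code is 1.
- **Cut.** A median split takes its threshold from observed scores. This one is a number written into the plan, and it coincides with the middle of the wrong range.

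At stake are whether the form handed to participants matches the outcome to be analysed, and whether the reported range and any high/low classification are correct.

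**Working it through.** **Inputs.** Six items and four response options (section 7d, Measurements). Codes from 1 to 4, and nine printed items (Appendix C). Stated range 0–24 and cut 0–11/12+ (section 7d, Measurements).

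**Formula.** For a sum score on a complete form, minimum = items × lowest code and maximum = items × highest code. With integer codes, possible totals = maximum − minimum + 1, and midpoint = (minimum + maximum) / 2.

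**Step 1: try to reproduce the stated 0–24.**

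| Items | Codes | Options | Range | Possible totals | Midpoint |
|---|---|---|---|---|---|
| 6 | 1–4 | 4 | 6–24 | 19 | 15 |
| 6 | 0–3 | 4 | 0–18 | 19 | 9 |
| 6 | 0–4 | 5 | 0–24 | 25 | 12 |
| 9 | 1–4 | 4 | 9–36 | 28 | 22.5 |
| 9 | 0–3 | 4 | 0–27 | 28 | 13.5 |

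Only six items coded 0–4 give 0–24. That needs five options, against the four in the text and the 1–4 coding on the form. No four-option version reproduces the figure.

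**Step 2: find which bound is wrong.** Six items at 1–4 give a maximum of 6 × 4 = 24, which agrees with the plan, and a minimum of 6 × 1 = 6, which does not. The lower bound is the error.

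**Step 3: could totals of 0–5 arise from blanks?** If a blank scored 0, the lowest total would be 6 minus the number of blanks. A total of 5 would need at least one blank, and 0 would need all six blank. The documents state no such rule.

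**Step 4: which items are meant to be scored?** Nine items at 1–4 would reach 9 × 4 = 36. The stated maximum of 24 rules that out, and the text lists exactly the circumstances in items 1–6. The intended score is therefore items 1–6.

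**Step 5: the cut.** The midpoint of 0–24 is (0 + 24) / 2 = 12, where the high class begins. The midpoint of 6–24 is (6 + 24) / 2 = 15.

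| Range | Low totals (up to 11) | High totals (12 or more) |
|---|---|---|
| 0–24 as stated | 12 (0 to 11) | 13 (12 to 24) |
| 6–24 as coded | 6 (6 to 11) | 13 (12 to 24) |

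These count possible totals. They are not shares of participants, which the documents cannot give.

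**The case against.** The strongest reply is that the plan already settles the scoring. Section 7d calls the instrument modified, says it has six items, lists them and gives a maximum that nine items would exceed. The sentence introducing the instruments leads into that list, and Appendix C is only a parenthetical pointer. The mixed model uses the continuous score, so neither the stated minimum nor the cut enters the main analysis. Much of this stands, and it limits what may be inferred.

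- **That the primary outcome is undefined.** A reader might infer this from the nine-item form. The text does not support it: an analyst following section 7d would sum items 1–6.
- **That blanks in items 7–9 would trigger imputation.** Section 7d (Data Management) speaks generally of missing data. Nothing there counts items outside the score as missing outcome data.
- **That participants are forced to answer inapplicable questions.** Appendix C as available shows an anchor line and a list of items, without the response boxes printed for the OHIP-14. Layout may have been lost, so what respondents would see cannot be established.
- **That the cut was invented without data.** The preceding sentence reports a reliability coefficient of 0.91 in the past tense, so the cut may also come from earlier work. What can be said is that it was fixed before this trial's data and that its origin is unclear.
- **That the treatment comparison is biased.** No mechanism is shown that would make the three extra items or the wrong minimum act differently between arms.

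The reply does not remove the discrepancy itself. The form to which the plan points still differs from the definition, and the printed range is still unattainable on complete forms.

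**Conclusion.** The point holds as an inconsistency between text and form, together with an arithmetic error in one bound. Three of the nine printed items fall outside the definition of a primary outcome. The range on complete forms is 6–24 (19 possible totals), not 0–24 (25 possible totals). The high/low cut is misdescribed as a median split and sits 3 points below the midpoint of the correct range (15 − 12 = 3).

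The figure 6–24 rests on three assumptions: the six-item definition governs, the form's 1–4 coding is used, and a blank is not scored as 0. The stated maximum of 24 supports the first two.

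The consequence is limited. The continuous comparison is not biased by a wrong stated minimum, no effect on power or error rate is shown, and the cut matters only if the dichotomy is used, which the Data Analysis section does not do. The correction is still worth making, because it changes the form given to participants and a stated property of a primary outcome at almost no cost.

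**What to change.** 1. Remove items 7–9 from the Appendix C form. If data collection has begun, state instead that these items are not scored.
2. In section 7d (Measurements), define the score as the sum of items 1–6, each coded 1–4, with range 6–24.
3. Delete the 0–11/12+ dichotomy, or keep it for description only, split at the observed baseline median.
4. Leave the continuous score as the primary analysis.

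A rule for missing items among the six, such as proration, would be useful but is optional; this correction does not depend on it.

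The cost is three lines removed from one form and a few sentences edited in one paragraph. Table 1 in section 7c places baseline collection in Summer–Fall 2017, but the documents do not show whether it had started. If it had, the scoring note is enough and no data need be collected again.

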### **4) Objectives**

- **Primary Objective:**

The objective of this study is to test the efficacy of an oral health education group based activity versus an individual oral health education activity in terms of changes in oral health related quality of life (OHRQoL), self-efficacy and oral health knowledge.

- **Secondary Objective**

The secondary objective of this study is:

a) To assess differences among intervention and control groups by senior's oral health knowledge.

- **Overall Hypotheses**

Ho: There are no significant differences in the selected behavioral outcome measures between the interventions, either group-based or individual based education and the control.

Ho: The two educational interventions are not equivalent in the selected behavioral outcome measures.

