### **Control Group: (60 seniors).**

Seniors who are randomly assigned to the control group will continue receiving regular dental care under the standard clinic operation. Subjects in this group will complete intake forms to assess main behavioral outcomes, at baseline and after 12 months. No other activities will be conducted in this group.

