### **Data Analysis:**

Initial analyses will be conducted to determine normality of distributions of the continuous variables, and any necessary transformations will be conducted. Primary outcomes will be the OHIP 14 and the self-efficacy scores. All eligible patients will be randomly assigned to 1 of the 3 groups described above. Although randomization should provide relatively comparable groups, demographic variables that differ between groups and are correlated with the primary outcomes will be used as covariates. Preliminary analysis will include measures of central tendency and dispersion, as well as an examination of the bivariate relationships among the primary and secondary outcome variables, potential moderators, and demographic characteristics.

Differences between the groups on baseline demographic, and psychological measures will be examined using  $\chi^2$  (Pearson) or Student's *t*-tests, as appropriate. Moreover, differences on the variables listed above among completers and drop-outs will also be explored. Intention to treat (ITT) analyses will then be conducted.

OHIP 14 and self-efficacy scores will be the primary outcomes. Initially, we will assess the differences between the interventions and control using 2-sample *t*-tests. The main analysis will be based on linear mixed-effects models for repeated measures (using the OHIP 14 and self-efficacy scores as continuous outcome variables) to assess differences between intervention and control groups. Similar analyses will be conducted for secondary outcome measures. Statistical significance will be set at  $p < .05$ .

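### Oral health knowledge is timed by the intervention rather than by month, so its follow-up point is undefined for control and not aligned for Intervention Group 2

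*Combined protocol and SAP*

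**What the plan says.** All references are to the combined protocol and SAP.

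- **Section 4, Objectives.** The single secondary objective is "To assess differences among intervention and control groups by senior's oral health knowledge". The primary objective also compares the two education formats "in terms of changes in oral health related quality of life (OHRQoL), self-efficacy and oral health knowledge".
- **Section 7d, Measurements.** The knowledge questionnaire "will be used to assess the oral health information/knowledge of the seniors pre and post intervention". It is the only instrument in that list with a timing rule of its own, and no section turns the rule into a month.
- **Section 7d, Control Group.** "Subjects in this group will complete intake forms to assess main behavioral outcomes, at baseline and after 12 months". The next sentence reads "No other activities will be conducted in this group".
- **Section 7d, Intervention Group 1.** Two group sessions take place within 12 months. Forms are completed before the first session and at months 6 and 12.
- **Section 7d, Intervention Group 2.** The individual education is first said to run over 12 months. The three dental visits are then spread over 18 months. Forms are completed before the first session, at each follow-up visit (no months given) and after 18 months. The Abstract gives 18 months for this arm.
- **Section 7d, Data Analysis.** "Primary outcomes will be the OHIP 14 and the self-efficacy scores". Secondary outcomes are to be analysed in a similar way, with two-sample t-tests and then a linear mixed model for repeated measures. No month is named for any comparison.

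**The concern.** A comparison with control needs a follow-up time that exists in every arm. Timing by the intervention does not supply one, because controls receive no study education. The calendar forms could fill the gap, but they are described as covering the main behavioral outcomes, a term the plan never defines. Objectives counts knowledge among the outcomes, whereas the objective restated at the start of Study Procedure names only quality of life and self-efficacy. Site staff could read this either way.

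Two things are at stake. If the questionnaire were left out of the control forms, the missing scores could not be recovered at analysis. If it is included, the last score in Intervention Group 2 still comes later after baseline than the last score in the other two arms. A difference in final scores could then reflect longer follow-up, a different format of education, or both.

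**Working it through.** The plan gives no effect size, standard deviation, power or dropout rate, so there is no sample-size calculation to reproduce. The check consists of the arm counts and a side-by-side reading of the schedules.

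**Arm counts (Section 7d).** Control 60, Intervention Group 1 60, Intervention Group 2 70, of whom 10 are for calibration only.

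- Total: 60 + 60 + 70 = 190, which matches the stated sample.
- Seniors to be compared: 190 − 10 = 180, or 60 per arm.
- Control share: 60/180 = 33.3%.

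**Schedules, in months from baseline.**

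| Arm | Study education | Dated forms | Undated forms |
|---|---|---|---|
| Control | none | 0, 12 | none |
| Intervention Group 1 | 2 sessions within 12 months | 0, 6, 12 | none |
| Intervention Group 2 | 12 or 18 months, both stated | 0, 18 | each follow-up visit |

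**Reading A: knowledge follows the intervention.** Control has no point after an intervention. In Intervention Group 1 the point falls after a second session whose date is not given. In Intervention Group 2 it falls after a programme with two stated lengths. No common month results.

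**Reading B: knowledge follows the calendar forms.** The dated months shared by each pair of arms are:

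- Control and Group 1: {0, 12} ∩ {0, 6, 12} = {0, 12}. There is a common follow-up at month 12.
- Control and Group 2: {0, 12} ∩ {0, 18} = {0}. Only baseline is shared.
- Group 1 and Group 2: {0, 6, 12} ∩ {0, 18} = {0}. Only baseline is shared.

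Two of the three pairs thus have no guaranteed common follow-up, and their final forms are 18 − 12 = 6 months apart. If an undated Group 2 visit fell at month 12, the control and Group 2 set would become {0, 12} and the problem would disappear. Nothing in the plan requires such a visit.

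**Consequence for the analysis.** A t-test on final scores would compare month 18 in Group 2 with month 12 elsewhere. The mixed model does not remove this by itself. If time is categorical, month 18 has no control counterpart. If time is continuous, the contrast relies on an assumed shape of change over time, and control has only two points to support it.

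**Calendar check (Section 7c, Table 1).** Baseline is in Summer–Fall 2017 and follow-up in Spring–Summer 2018. Eighteen months after the start of summer 2017 is about the end of 2018, later than the follow-up window and the manuscript date of Fall 2018. The table's dates are approximate, but they too need reconciling with the 18-month form.

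**The case against.** The strongest reply is that the wording is ordinary shorthand for baseline and follow-up. Measurements lists knowledge beside OHIP-14 and self-efficacy as an outcome measure for the study and does not limit it to the education arms. All the instruments sit together in Appendix C. Objectives names knowledge in the primary objective. On this view knowledge is one of the outcomes on the control forms, and control and Intervention Group 1 can be compared at month 12.

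Most of this stands. It is the more natural reading, and it rules out two stronger inferences.

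- A reader might infer that controls cannot be scored, pointing to "No other activities will be conducted in this group". That sentence follows the form schedule and most naturally means that controls receive no education sessions. It does not exclude a questionnaire.
- A reader might infer that the education arms are tested straight after teaching, so that short-term recall is set against a 12-month control score. No section places the questionnaire immediately after a session, and the plan gives no figures on retention. That scenario and any effect size attached to it are unsupported.

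It can also be said that the 12- versus 18-month conflict is not specific to knowledge. That is correct: OHIP-14 and self-efficacy are misaligned in the same way. What is particular to knowledge is its own undated timing rule and the fact that its place on the calendar forms is never stated.

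The reply does not repair the schedule of Intervention Group 2. Even if every arm completes the questionnaire with its forms, this arm has no dated follow-up in common with either of the others.

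**Conclusion.** The point holds as a gap in the definition of the endpoint and a misalignment between arms. It does not show that the knowledge comparison is impossible. The stated time point has no literal meaning for 60 of the 180 seniors (33%). Two of the three pairwise comparisons have no guaranteed common follow-up, and final forms differ by 6 months. The comparison of control with Intervention Group 1 is sound if knowledge is on the 12-month forms, which is likely but unstated.

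This rests on reading the Group 2 follow-up visits as undated and its 18-month form as its last. It would lapse for Group 2 if a visit were fixed at month 12. The documents do not allow the direction or size of any bias in the knowledge score to be estimated. The change is worth making before data collection, because scores not collected at a common time cannot be restored later.

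**What to change.** 1. In Measurements, replace the intervention-based timing with collection at baseline and month 12 in all three arms.
2. List the 15-item questionnaire by name in the assessments of Control, Intervention Group 1 and Intervention Group 2.
3. In Data Analysis, name month 12 as the time point for the knowledge comparison. Treat scores at other times, including month 18 in Intervention Group 2, as supportive.
4. Reconcile the 12- and 18-month statements for Intervention Group 2, and check the result against Table 1. Which programme length is intended is for the investigators to settle. Items 1 to 3 concern only when the outcome is measured.
5. Apply the same alignment to OHIP-14 and self-efficacy, which share the problem.

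**Cost.** For control and Intervention Group 1 the change is wording, plus a few minutes per control if the form was not already included. Intervention Group 2 needs a dated month-12 questionnaire. This can be done at an existing follow-up visit if one falls then; otherwise it needs a separate contact. Table 1 may also need a later follow-up window, since 12 months after a fall 2017 baseline is fall 2018.

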### **Calibration:**

For purposes of calibration and assuring treatment fidelity of the dental public health hygienist when delivering the MI oral health session (Intervention 2), 10 patients will be recruited and consented to receive this intervention only. The sessions with these patients will be audio recorded so that research staff can check treatment fidelity and provide feedback to the hygienist as appropriate before data collection starts. These 10 patients will not be part of the research study and will be offered a \$30 dollar visa gift card for

